4. SAMPLE SIZE CONSIDERATIONS

The value of possible predictors will be assessed through the construction of Receiver Operating Characteristics (ROC) curves, and calculation of negative predictive value. Based upon register data from the outpatient clinical at Ahus, the prevalence of cardiac disorder in the population under study is estimated at 2 %. The area under the ROC-curve for NT-proBNP in a previous study with similar methodology has been established at 0.85 (Law et al, 2009). The possible clinical application of the results from the present study requires a very low risk of false negatives (ie. no patients with cardiac disorders should be deemed healthy based upon a certain cardiac marker). Therefore, the level of significance (α) is set to 0.01. Given a test power ($1 - \beta$) = 0.8, sample size is estimated at 400 patients. A drop-out rate of up to 20 % might be assumed (technical problems, refusal of blood sampling, etc), therefore a total of 500 patients should be included in the study.

In part 2, when a population of 125 patients with well-defined CHD is added to the population of about 500 individuals previously recruited, the ratio of cases:controls increases to about 0.25. This will enable an α -value less than 1×10^{-10} , and a power ($1 - \beta$) of comparable magnitude, which we find satisfactory.

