6. STATISTICAL METHODS

General considerations

Continuous variables will be reported with parametric (mean/standard deviation) or non-parametric (median, quartiles) descriptive statistics, depending on the distribution. Ordinal/nominal variables will be reported as frequency tabulation. All statistical tests will be carried out two-sided. A p-value ≤ 0.05 is considered statistically significant throughout.

Predictor analysis

In part 1, the relationship between each potential predictor variable and the primary outcome variable will first be explored in univariate logistic regression analyses. Collinearity between predictor variables will be assessed by correlation analyses, and dimensionality reduction by PCA will eventually be considered. Then, all variables with a p-value ≤ 0.25 in the univariable analyses will be included in the first modelling step. In order to obtain a more parsimonious model, the combination of variables that gives the lowest Akaike Information Criteria (AIC) will constitute the final model. The value of predictor(s) in the final multivariable model will be assessed through the construction of Receiver Operating Characteristics (ROC) curves, and calculation of negative predictive value.

In part 2, the prediction model from part one will be validated by including a total of n~125 individuals with known CHD in the study population. The prediction model should correctly classify all these cases; if not, the model will be adjusted. We aim for zero false negatives, i.e. all cases with cardiac abnormalities in need of intervention and/or hospital follow-up should be identified. To explore the potential of the prediction model to classify all cases based upon this premise, we will apply different combinations of levels of the identified predictor variables.

Cross-sectional analyses

For the secondary study aims, cross-sectional analyses across cases and controls are feasible. Such analyses will feature parametric tests (Student t), non-parametric tests (Mann-Whitney), regression analyses or table analyses (Chi-square, Fisher) as appropriate.

Sensitivity analyses

Throughout, sensitivity analyses applying a different classification of caseness in the primary outcome variable will be carried out:

1. Caseness defined as all abnormalities identified by echocardiography, independent of intervention/follow-up needs
2. Caseness defined as all abnormalities in need of surgical or catheter-based intervention

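### The strict α of 0.01 is presented as protection against missed cases, which it does not give; with about 8 expected cases, part 1 is not sized for that aim

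*SAP*

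**What the plan says.** SAP section 4 states that possible clinical application "requires a very low risk of false negatives", which it explains as no child with a cardiac disorder being called healthy on the strength of a marker. The next sentence reads: "Therefore, the level of significance (α) is set to 0.01". With power 0.8, an AUC of 0.85 for NT-proBNP from an earlier study, and the statement that "the prevalence of cardiac disorder in the population under study is estimated at 2" %, it arrives at 400 children, raised to 500 for drop-out of up to 20%. No null AUC, target sensitivity or interval width is given. For part 2, section 4 claims an α below 1×10⁻¹⁰ and a power (1 − β) "of comparable magnitude, which we find satisfactory".

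Section 6 (Predictor analysis) screens predictors at p ≤ 0.25 in part 1, after which "the combination of variables that gives the lowest Akaike Information Criteria (AIC) will constitute the final model". Performance is to be described by ROC curves and "calculation of negative predictive value". For part 2 it says: "The prediction model should correctly classify all these cases; if not, the model will be adjusted". It then adds: "We aim for zero false negatives", with cases defined as abnormalities needing intervention or hospital follow-up. No confidence interval for sensitivity is planned.

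**The concern.** The false-negative requirement concerns sensitivity at a chosen cut-off: of the children with disease, how many fall on the healthy side. The α in section 4 belongs to a different question, namely whether the AUC exceeds some null value. A marker can pass that test comfortably and still miss a substantial share of cases. The word linking the two sentences therefore claims a protection that the calculation does not contain.

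This matters because it is the only safety argument offered for the part 1 sample size, and section 3 intends the model for general practice. At 2% prevalence, part 1 is expected to contain about 8 cases. With no interval for sensitivity in the plan, detecting all of them could be reported as meeting the zero-miss aim, although so few cases cannot exclude a high miss rate.

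**Working it through.** **Inputs from the SAP.** Section 4: α = 0.01, power 0.8, AUC 0.85, prevalence 2% (1 case to 49 controls), drop-out 20%, 125 added cases in part 2. Section 6: tests are two-sided. Assumed: null AUC 0.5, because none is stated.

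**1. Reproducing the 400.** Hanley-McNeil variance for m cases and n controls:

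Var(A) = [A(1 − A) + (m − 1)(Q₁ − A²) + (n − 1)(Q₂ − A²)] / (mn), with Q₁ = A/(2 − A) and Q₂ = 2A²/(1 + A).

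Power = Φ[(0.85 − 0.5 − z·SE₀)/SE₁], with z = 2.576 for two-sided 0.01.

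- 8 cases, 392 controls (400): SE₀ = 0.1032, SE₁ = 0.0859, power 0.836.
- 7 cases, 343 controls (350): SE₀ = 0.1104, SE₁ = 0.0919, power 0.763.

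With whole cases, 0.8 is first reached at 400, so the stated figure is reproduced; 400/0.8 = 500. The null need not be exactly 0.5: a two-sided test against 0.51 (power 0.801), or one-sided tests against 0.52 (0.845) or 0.53 (0.811), also first reach 0.8 at 400.

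**2. What the stricter α buys.** At two-sided α 0.05 (null 0.5), 4 cases (200) give power 0.699 and 5 cases (250) give 0.806. Moving from 0.05 to 0.01 therefore raises the expected number of cases from 5 to 8 and does nothing else for sensitivity.

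**3. What the cases can show.** If all k cases are detected, the exact two-sided 95% lower limit for sensitivity is 0.025^(1/k).

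| Cases, none missed | Lower limit |
|---|---|
| 3 | 29% |
| 5 | 48% |
| 8 | 63% |
| 10 (2% of 500) | 69% |
| 14 | 77% |

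The rows for 3 and 14 are the 2.5 and 97.5 percentiles of a binomial count with n = 400 and probability 0.02. All these limits are best cases, since predictors, model and cut-off are chosen on the same data.

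**4. How often a poor rule would look perfect.** For a fixed rule with true sensitivity s, P(no miss) = s^k.

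- s = 0.8: 0.8⁸ = 0.168; 0.8¹⁰ = 0.107.
- s = 0.9: 0.9⁸ = 0.430.

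**5. NPV.** Calling every child healthy gives 98% at 2% prevalence. An illustrative test with sensitivity 50% and specificity 80% (values not from the SAP) gives 0.98·0.8/(0.98·0.8 + 0.02·0.5) = 0.784/0.794 = 98.7%. A test that misses half the cases therefore moves NPV by less than one percentage point.

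**6. Part 2.** With 125 cases, 500 controls, null 0.5 and two-sided α 10⁻¹⁰ (z = 6.467): SE₀ = 0.02889, SE₁ = 0.02242, β = 1.7×10⁻¹³. The claim is therefore achievable, but it concerns the same AUC test. Read literally, a power comparable with 10⁻¹⁰ would be almost zero; β is presumably meant. For missed cases, 125 of 125 would give a lower limit of 0.025^(1/125) = 97.1%, but only for a rule fixed before those children are classified.

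**The case against.** The strongest reply is that section 6 states the zero-miss aim in its part 2 paragraph, where about 125 cases are added, so the aim will not be judged on 8 children. That part 1 would be over-reported is a prediction, not something the plan says. This does not rescue the rationale. Section 4 itself ties false negatives to the α used for part 1. The aim in section 6 covers children needing follow-up as well as intervention, whereas all part 2 cases are scheduled for intervention. And the model may be adjusted on those same cases until it classifies them, so a final 125 of 125 could be obtained by construction.

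A second reply is that 400 and 500 are right and that deleting one link changes no analysis. The first half is true: the fault lies in the assurance attached to a correct calculation. The remedy goes further than the deletion, however, because no interval for the quantity that the plan cares about most is currently specified.

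Three limits are fair. The figure of 8 cases is an expectation, and the register prevalence of 2% may not have used the caseness criteria in Table 2, so reported intervals must come from observed counts. The preference for sensitivity over NPV as the lead measure is partly judgement, although the 98% no-test figure follows directly from the SAP. Finally, section 4 sizes at 0.01 while section 6 uses 0.05 throughout; that mismatch is separate and should be reconciled in the same edit.

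**Conclusion.** The concern holds. α = 0.01 does not limit missed cases, and part 1 is not sized for the false-negative aim. With 8 expected cases and none missed, up to 37% of cases could still be missed within the exact 95% interval (31% with 10 of 10), and both figures are optimistic because the model is selected on the same data. The result rests on the SAP's own 2% prevalence. The null AUC of 0.5 is assumed and matters only for reproducing the 400 and for the comparison with α 0.05; the sensitivity bounds do not depend on it. This should be corrected before analysis, since the plan as written attaches an assurance to part 1 that its data cannot provide.

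**What to change.** **Section 4**
- Delete the link between α and false negatives.
- State the null AUC, and that 400 (500 enrolled) is sized to show discrimination better than that null.
- State that part 1 is not sized for the false-negative aim: at the expected counts, 8 of 8 gives at best 63–100% and 10 of 10 at best 69–100%.
- Correct the power wording for part 2, and reconcile 0.01 with the 0.05 in section 6.

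**Section 6**
- Beside the ROC curve, lead with sensitivity and its exact confidence interval from the observed cases, and specificity at the same cut-off.
- Report NPV only at part 1 prevalence, next to the 98% of a no-test strategy.
- Quote an exact interval for part 2 only if model and cut-off are locked before those cases are classified (125 of 125 would give 97.1–100%, for intervention-level disease only). After any adjustment on those cases, call the figure apparent sensitivity and omit that interval.

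**Cost.** SAP wording and one added reporting line, with no extra patients. The stated assurance becomes less favourable, and a valid part 2 interval requires locking the model first.

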5. ANALYSIS SETS

Full analysis set

The 'full analysis set' is defined as all participants who were subsequently included in the two parts of the study. Missing values will be imputed based on the principle of 'mean substitution'.

Cardiac murmurs in children: Predictive value of cardiac markers (CAMUS)

Per protocol analysis set

The ‘per protocol analysis set’ is defined as all patients in the ‘full analysis set’ that completed the investigational program without any of the following protocol deviations:

- Primary outcome missing

Missing data will not be imputed in the per protocol analysis set.

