1. DESIGN

Design overview

Cardiac murmurs in children: Predictive value of cardiac markers (CAMUS) is an observational study on spontaneously discovered cardiac murmurs in children. The primary aim is to establish the predictive value of cardiac markers for identification of cardiac disease in children with heart murmurs. NT-proBNP and hs-troponins are considered the most relevant cardiac markers. Secondary aims are: a) To establish age-adjusted reference range for cardiac markers in children, and b) To explore aspects of cardiovascular physiology in children.

In part 1 of the project, a total of ~500 individuals aged 4 weeks to 10 years will be consecutively recruited among those referred to the Dept. of Paediatrics and Adolescent Medicine, Akershus University Hospital (Ahus) for assessment of heart murmurs. The protocolized investigational program of the study includes clinical examination, symptom assessment, pulse oximetry, blood sampling, ECG recording, and echocardiography. A definite diagnosis of cardiac disease or not will be based upon the echocardiographic examination, hence serving as the “gold standard”.

In part 2 of the project, a total of ~125 individuals aged 4 weeks to 10 years with confirmed congenital heart disease (CHD) and scheduled for intervention at OUS Rikshospitalet will be included. They will undergo the same investigational program as in part 1. A main purpose of part 2 is to validate the prediction model developed in part 1.

Table 1. Criteria for inclusion and exclusion

Inclusion criteria	Exclusion criteria
Spontaneously discovered heart murmur at general practitioner's office (part 1)	Known cardiac disease (part 1 only)
Confirmed cardiac anomaly and scheduled for intervention at OUS Rikshospitalet (part 2)	Other chronic or acute disorder (part 1 only)
Age > 4 weeks, < 10 years	Medications (part 1 only)

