2. ENDPOINT

Outcome variable

The primary outcome variable in part 1 is a diagnosis of cardiac disease based upon echocardiographic assessment. The diagnostic process will adhere to international consensus guidelines on paediatric cardiology (Doshi & Chikkabryappa, 2018; Sachdeva et al., 2020; Writing Committee et al., 2021). Thereafter, all participants will be assigned to either of two groups: a) A cardiac diagnosis that needs intervention/treatment and/or further clinical follow-up (cases); b) No cardiac diagnosis or a cardiac

Cardiac murmurs in children: Predictive value of cardiac markers (CAMUS)

diagnosis that does not need intervention/treatment and/or further clinical follow-up (controls). Hence, the primary outcome variable is dichotomous. The assignment to cases vs. controls will follow pre-defined criteria pertaining to each cardiac diagnosis/diagnostic group (Table 2).

In part 2, all participants are assigned as cases, as per the inclusion criterium of a confirmed cardiac anomaly in need of intervention.

Table 2. Criteria for assignment of cases (need of intervention and/or clinical follow-up) vs. controls (no need of intervention nor clinical follow-up)	
Primary cardiac diagnosis	Criteria for caseness (only one criterium needs to be fulfilled per diagnosis)
Persistent foramen ovale (PFO)	N/A (never assigned as case)
Atrial septal defect (ASD), all subgroups	Case if: 
 - Ostium premium defect - Sinus venosus defect - Ostium secundum defect diameter > 3 mm OR with signs of right atrium volume load.
Persistent ductus arteriosus (PDA)	Case if: 
 - Ductus diameter >1.5 mm. - LA/Ao ratio >1.5 - Retrograde diastolic flow in the abdominal aorta. - Continuous murmur
Ventricular septum defect (VSD), all subgroups	Case if 
 - Perimembranous location - Inlet location - Subpulmonary outlet/supracristal location - Muscular location with diameter >5 mm OR left ventricular dilatation OR Qp/Qs ≥1.5. - Multiple defects
Aortic valve pathology (stenosis (AS), regurgitation (AR), bicuspid valve)	Case if: 
 - Flow velocity ≥ 2.0 m/s. - Hypertrophy of left ventricle. - Aortic regurgitation (more than trivial)

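### The full analysis set fills every missing value with a single mean, the per protocol set fills none, and the SAP does not say which set carries the main result

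*SAP*

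**What the plan says.** SAP section 5 defines two analysis sets.

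- The full analysis set is "all participants who were subsequently included in the two parts of the study". For it, "Missing values will be imputed based on the principle of" mean substitution. No variable is exempted, outcome and predictors are not separated, and the group over which the mean is taken (age band, study part or pooled) is not stated.
- The per protocol set removes children with one listed deviation, "Primary outcome missing". For it the rule is the opposite: "Missing data will not be imputed in the per protocol analysis set".

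Section 6 does not say which set the predictor analysis uses, and no section names a primary set.

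Three other places bear on this. Section 4 sizes part 1 at 400, raised to 500 for drop-out of up to 20%, and lists refused blood samples among the causes of drop-out. Section 2 states of the diagnosis: "Hence, the primary outcome variable is dichotomous". Section 1 gives as a secondary aim "To establish age-adjusted reference range for cardiac markers in children".

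**The concern.** NT-proBNP is one of the two markers that section 1 treats as most relevant, and section 4 foresees that some blood samples will be refused. Under the full-set rule, all children without a marker value get the same number, and the analysis then treats it as a measurement. Filled cases and filled controls are tied, so the marker separates the groups less well than it really does.

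Three things are at stake.

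- **The headline result.** Two sets with opposite missing-data rules and no named primary set leave the main AUC and negative predictive value open until the data have been seen.
- **The part 2 check.** Section 6 aims for zero false negatives and will adjust the model if a part 2 case is misclassified. A case with a filled marker would be judged on a value that was never measured.
- **Consistency with the sample size.** Section 4 counts a refused blood sample as a loss, whereas section 5 keeps that child with a filled value.

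**Working it through.** **The plan's own figures.** 400 / (1 − 0.20) = 500 reproduces. The 400 also reproduces with AUC 0.85 against 0.5 (null value assumed), two-sided alpha 0.01, power 0.80 and 49 controls per case: the binormal formula gives 7.29 cases, rounded up to 8, and 8 × 50 = 400. Expected part 1 cases are 0.02 × 500 = 10, leaving 490 controls. With part 2 added there are 10 + 125 = 135 cases in 625 children (21.6%).

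**Inputs for the AUC under mean filling.** From section 4: AUC 0.85 and prevalence 2%. Assumed: a binormal marker with equal variances; shares missing m0 in controls and m1 in cases; the mean taken on the log scale, or on the raw scale with a log-SD of 0.7–1.0. The SAP gives no rate of missing markers, so 5%, 10% and 20% are illustrations. The 20% is an upper one, borrowed from the all-cause drop-out bound.

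**Formula.** Separation d = √2 × Φ⁻¹(0.85) = 1.466. With c the filled value:

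AUC = (1−m0)(1−m1) × 0.85 + (1−m1) m0 P(case > c) + m1 (1−m0) P(control < c) + 0.5 m0 m1

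**Example: part 1, log scale, 10% missing in both groups.** c = 0.02 × 1.466 = 0.029 control SDs above the control mean. P(case > c) = Φ(1.466 − 0.029) = 0.925 and P(control < c) = Φ(0.029) = 0.512.

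AUC = 0.81 × 0.85 + 0.09 × 0.925 + 0.09 × 0.512 + 0.5 × 0.01 = 0.823

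**Results over the log-scale and raw-scale means.**

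| Missing (controls / cases) | Part 1 mean | Pooled mean |
|---|---|---|
| 5% / 5% | 0.837–0.841 | 0.840–0.841 |
| 10% / 10% | 0.823–0.831 | 0.828–0.832 |
| 20% / 20% | 0.794–0.809 | 0.804–0.810 |
| 20% / 2% | 0.839–0.858 | 0.808–0.848 |
| 2% / 20% | 0.783–0.821 | 0.801–0.843 |

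In the first three rows complete cases keep 0.85. In the fourth row the filled AUC can exceed 0.85, so the direction is not fixed.

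**Scale.** Hanley–McNeil with A = 0.85, A/(2−A) = 0.7391, 2A²/(1+A) = 0.7811 and A² = 0.7225:

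- Part 1 (10 cases, 490 controls): variance = [0.1275 + 9 × 0.0166 + 489 × 0.0586] / 4900, so SE = 0.077. The loss at 20% missing is 0.041–0.056, or 0.5–0.7 SE.
- Pooled (135 cases, 490 controls): SE = 0.022. The loss is 0.018–0.022 at 10% (about 1 SE) and 0.040–0.046 at 20% (about 2 SE). This assumes that 0.85 also holds with part 2 children included.

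**More than one predictor.** In a simulated logistic model with a second predictor of AUC 0.60 or 0.70 (assumed), full-data AUC was 0.85–0.88. Filling only the marker cost about 0.01 at 5% missing, 0.01–0.03 at 10% and 0.03–0.05 at 20%. The effect on AIC selection was not computed.

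**Artificial false negatives.** The part 1 log-scale mean lies below about 92% of true case values; the raw-scale mean lies below about 82–86%. A case filled with it looks more like a control than most cases do.

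**Reference ranges.** If filled values were used, the marker SD would shrink to √0.9 = 0.949 of its true size at 10% missing and √0.8 = 0.894 at 20%. The SAP does not say which set serves this aim.

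**The case against.** The strongest reply is that the SAP already contains an unimputed set that drops children without a diagnosis, so the pair works as a built-in sensitivity comparison. That would hold if one of the two were named as primary. As none is, the choice stays open.

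The second reply is that the effect is small where the model is built. This stands: in part 1 even 20% missing moves the AUC by less than one standard error, and with equal missingness the marker is understated, not flattered. Because section 4 treats refused samples as drop-outs, the authors may also never have meant to analyse these children with filled values. Section 5 nevertheless says otherwise.

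Two stronger readings are tempting and are not supported.

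- **That diagnoses will be filled with a fraction.** Taken literally, a missing part 1 diagnosis would become 10/500 = 0.02, or 135/625 = 0.216 pooled. Section 2 assigns every child to one of two groups by set criteria, and a fractional status would stop a ROC analysis at once, so an exclusion left unwritten is the likelier explanation. Part 2 is untouched, because "In part 2, all participants are assigned as cases". What remains is a wording gap.
- **That ignoring age is the main harm.** In an illustration with 10% missing and an assumed age slope of 0.5 or 1.0 marker SD per SD of age, filling by age instead of by the overall mean recovered only about 0.002–0.008 of AUC. Most of the loss comes from filling with a single value at all.

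**Conclusion.** The concern holds in a limited form and should be fixed. Section 5 prescribes a poor method for missing markers in one of two sets, and nothing says which set gives the result. Under missingness completely at random, a single-marker AUC of 0.85 falls by about 0.01 at 5% missing, 0.02–0.03 at 10% and 0.04–0.06 at 20%. That is within sampling error in part 1 and about one to two standard errors in the pooled data at 10–20%. The figures rest on a binormal marker, on assumed missing rates, and for the pooled data on carrying 0.85 over to part 2. If cases and controls differ in missingness, the direction can change.

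The conflict between sections 4 and 5 over refused blood samples follows from the text alone. So does the lack of a written exclusion for a missing diagnosis in the full set; this second gap is minor. A reader should not infer that the reported AUC will be badly biased: that depends on which set is used and on how many markers are missing, and the SAP gives neither.

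**What to change.** 1. Name the primary analysis set for the predictor analysis, and align it with the drop-out assumption in section 4.
2. State that the primary outcome is never imputed, and that children without an echocardiographic diagnosis leave the predictor analysis in both sets.
3. Drop mean substitution. Use complete cases for the markers needed. Alternatively, for model development only, use multiple imputation from part 1 data with age, log-transformed biomarkers and the outcome in the imputation model. In that case, pre-state how AIC selection works across the imputed data sets, and report complete cases alongside, because about 10 cases support any imputation model only weakly.
4. Run the part 2 validation and the zero-false-negative check only on children with measured values of the predictors in the model, and report how many were excluded. Imputing here, even with a better method, would still test the model on unmeasured values, and using case status to do so would feed the answer into the predictor.
5. Do not impute biomarkers for the reference ranges.

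The cost is SAP wording, standard software, a little extra analysis if multiple imputation is chosen, and a somewhat smaller number in the validation check. No new data are needed.
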